9.2 Efficacy Assessments

9.2.1 Numeric Rating Scale of Pain Intensity (NRS)

The NRS of pain intensity is a unidimensional, segmented numeric version of the visual analog scale. A subject selects a whole number (0 to 10) that best indicates the intensity of his/her pain.

The format consists of a horizontal line which is anchored by terms defining pain levels where 0 represents no pain and 10 represents worst pain imaginable.

Subjects will report at bedtime their average pain intensity, worst pain intensity, and pain upon walking during the past 24 hours, using the 11-point NRS.

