5.1.5 Change from Baseline

If both post-baseline and baseline values are present/imputed, then change from baseline is defined as each post-baseline value – baseline value. Otherwise the change from baseline will not be reported.

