5.1.6 Percent Change from Baseline

If the baseline value is not equal to zero or missing and the change from baseline value is present/imputed, then the percent change from baseline is defined as 100 x (change from baseline / baseline) and is rounded off to 1 number after the decimal point. Otherwise the percent change from baseline will not be reported.

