9.1 Primary Efficacy Data

The primary efficacy data for this study is the NRS score assessing average pain intensity in the past 24 hours. Daily collected pain scores are based on an 11-point numerical rating scale/Likert scale ranging from 0 to 10. Where 0 represents no pain and 10 is the worst pain imaginable^[2].

The mean NRS score assessing average pain intensity in the past 24 hours will be calculated for the analysis visits described in Section 5.4.2^[4]:

- Baseline (average of Study Days -7 to -1)
- Week 1 (average of Study Days 1 to 7)
- Week 2 (average of Study Days 8 to 14)
- Week 3 (average of Study Days 15 to 21)
- Week 4 (average of Study Days 22 to 28)

The mean baseline visit will be calculated if at least 6 of the study days have a reported pain score. This is a requirement in order to be eligible for being randomized to a study drug treatment arm. There will need to at least 4 daily pain scores collected within a post-baseline analysis visit in order to calculate the mean pain score for that visit.

Each mean analysis visit score will take on values ranging from 0 to 10 and will be rounded off by one number after the decimal point. Data prior to Study Day -7 or after Study Day 28 will not be used in the mean calculated scores. No missing data imputations will be used for these observed means, but Section 9.1.3 will explain imputation methods used for sensitivity analyses.

The actual means, change from baseline, and percent change from baseline at each analysis visit will be summarized using descriptive statistics. The same descriptive statistics table will be additionally provided by each study site, age groups, gender, race, ethnicity, and subjects using or not using at least 1 concomitant analgesic medication at Baseline. All data collected and derived will be presented in subject listings.

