9.2.5 Short-Form McGill Pain Questionnaire, version 2 (SF-MPQ-2)

The SF-MPQ-2 measures the sensory, affective, and evaluative qualities of pain, including symptoms relevant to neuropathic pain. The tool includes visual analogue as well as verbal rating scales of pain intensity on a total of 22 neuropathic and non-neuropathic pain descriptors that are each evaluated on a 10-point numerical rating scale/Likert scale ranging from 0 to $10^{[12]}$. Where 0 represents none and 10 is worst possible.

The following questions that make up each published summary scale score [13]:

- Continuous Descriptors:
 - Throbbing Pain, Cramping Pain, Gnawing Pain, Aching Pain, Heavy Pain, and Tender
- Intermittent Descriptors:
 - Shooting Pain, Stabbing Pain, Sharp Pain, Splitting Pain, Electric-Shock Pain, and Piercing
- Neuropathic Descriptors:
 - Hot-Burning Pain, Cold-Freezing Pain, Pain Caused by Light Touch, Itching, Tingling or 'Pins and Needles', and Numbness
- Affective Descriptors:
 - o Tiring-Exhausting, Sickening, Fearful, and Punishing-Cruel

Each of the 4 summary scale scores will be calculated by the mean if more than 50% of the responses are available for the calculation. For example, the Continuous Descriptors summary scale score will need at least 4 of the 6 components available in order to calculate the mean. If all the 4 summary scale scores can be calculated, then the total pain score is computed by averaging the non-rounded 4 individual summary scale scores. If at least one summary scale score is missing, the total pain score will be set to missing. Each mean summary scale and total pain score will take on values ranging from 0 to 10 and will be rounded off by one number after the decimal point.

The secondary endpoints of interest with this data are the published summary scales and total pain scores change from baseline to Week 4. Subjects will be instructed to answer each question based on the pain and related symptoms they felt during the past week, so responses should be interpreted as cumulative over that time period. The SF-MPQ-2 will be assessed at the Baseline and Week 4/Early Termination visits.

The actual means and change from baseline will be summarized using descriptive statistics. ANCOVA analyses using the change from baseline to Week 4 will be provided for the published summary scales and total pain scores. The change from baseline to last post-baseline visit for each subject will also by summarized.

Protocol No.: NYX-2925-2001

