9.3.2 Responder Status Endpoints

Different efficacy responder statuses will be defined based on the following methods [4, 10]:

- Responder at $\geq 30\%$ Pain Reduction:
 - Subjects achieving ≥30% pain reduction on the mean NRS score assessing average pain intensity in the past 24 hours from baseline to Week 4 analysis visit and the subjects must complete the study. Subjects who do not have an analysis visit Week 4 mean NRS score assessing average pain intensity in the past 24 hours will be set to a non-responder.

- Responder at ≥50% Pain Reduction:
 - Subjects achieving ≥50% pain reduction on the mean NRS score assessing average pain intensity in the past 24 hours from baseline to Week 4 analysis visit and the subjects must complete the study. Subjects who do not have an analysis visit Week 4 mean NRS score assessing average pain intensity in the past 24 hours will be set to a non-responder.
- Responder at ≥30% Pain Reduction and Week 4 PGI-C Improved Score:
 - Subjects achieving ≥30% pain reduction on the mean NRS score assessing average pain intensity in the past 24 hours from baseline to Week 4 analysis visit and the subjects must complete the study. Subjects who do not have an analysis visit Week 4 mean NRS score assessing average pain intensity in the past 24 hours will be set to a non-responder.
 - o In addition, to be classified as "responders" subjects must have an analysis visit Week 4 PGI-C score of 1 (Very Much Improved) or 2 (Much Improved). Otherwise, those subjects will be set to non-responders.

The percent change from baseline that is \leq -30.0% is equivalent to \geq 30% pain reduction. Subjects with a calculated mean NRS score assessing average pain intensity in the past 24 hours at analysis visit Week 4 will be provided in a figure based on their percent change from baseline values. The horizontal axis displays a range of percentage-reductions from baseline at Week 4 in the mean NRS score assessing average pain intensity in the past 24 hours and the vertical axis displays the percentage of subjects achieving each of those levels of improvement. The horizontal axis will range from 0% to 100% in percentage-reductions and will not plot subjects with percentages below 0% (i.e. subjects that showed worse pain at Week 4 and the percentage change from baseline \geq 0%).

Frequency distributions, odds ratio, and relative risk analyses described in Section 5.3.5.5 will be used to summarize the responder status endpoints.

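### SAP 9.1 rounds the NRS means to one decimal before the 30% and 50% responder cuts, so some subjects at or near a cut get the wrong responder status

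*SAP*

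**What the plan says.** Protocol 9.2.1 has subjects record the NRS as a whole number from 0 to 10. SAP 9.1 averages the daily scores by week and states that each visit mean, baseline included, "will be rounded off by one number after the decimal point". On missing days it says: "The mean baseline visit will be calculated if at least 6 of the study days have a reported pain score". A weekly mean after baseline needs "at least 4 daily pain scores collected within a post-baseline analysis visit".

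The chain to responder status then runs as follows:
- SAP 5.1.5: "change from baseline is defined as each post-baseline value" minus the baseline value.
- SAP 5.1.6: percent change is 100 times change over baseline, "and is rounded off to 1 number after the decimal point".
- SAP 9.3.2: a percent change at or below minus "30.0% is equivalent to" a reduction of at least 30%. The 50% cut follows by analogy.

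None of these sections says that unrounded means are used. By contrast, the SF-MPQ-2 total in SAP 9.2.5 is "computed by averaging the non-rounded 4 individual summary scale scores".

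**The concern.** A seven-day mean of whole numbers is a number of sevenths and seldom has an exact one-decimal value. Rounding the baseline and Week 4 means first can move their ratio across a fixed cut. The subject's status then contradicts the endpoint itself, which is a reduction of at least 30% or 50%.

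Responder status is tested by chi-square or Fisher's exact test with odds ratios and relative risks (SAP 5.3.5.5 and 9.4), and its table (14.2.1.4.1) is marked for the topline. The composite of 30% reduction plus PGI-C (9.3.2) and the Week 4 condition of sustained reduction (9.3.4) take over the same status. Anyone recomputing responders from the listed daily scores could get different counts.

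**Working it through.** The plan states no figure for this point, so there is none to reproduce. The check compares status from unrounded values with status from the written chain.

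**Inputs.** Whole-number daily scores (Protocol 9.2.1); means and percent change rounded to 0.1 (SAP 9.1, 5.1.6); cuts at -30.0% and -50.0% (SAP 9.3.2). Assumptions: ties round away from zero, and the baseline mean lies between 4 and 9, because the randomization range is not shown.

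**Formula.** Let B and W be the seven-day totals.
- Unrounded reduction = 100 × (B − W)/B.
- Written chain: b = B/7 and w = W/7, each rounded to 0.1; then 100 × (w − b)/b rounded to 0.1.

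**Examples with complete diaries**

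| B to W | Unrounded reduction | b to w | Written chain | Status given |
|---|---|---|---|---|
| 40 to 28 | 12/40 = 30% | 5.7 to 4.0 | -1.7/5.7 = -29.8% | non-responder, wrong |
| 50 to 35 | 15/50 = 30% | 7.1 to 5.0 | -2.1/7.1 = -29.6% | non-responder, wrong |
| 43 to 30 | 13/43 = 30.23% | 6.1 to 4.3 | -1.8/6.1 = -29.5% | non-responder, wrong |
| 41 to 29 | 12/41 = 29.27% | 5.9 to 4.1 | -1.8/5.9 = -30.5% | responder, wrong |
| 34 to 24 | 10/34 = 29.41% | 4.9 to 3.4 | -1.5/4.9 = -30.6% | responder, wrong |
| 30 to 21 | 9/30 = 30% | 4.3 to 3.0 | -1.3/4.3 = -30.2% | responder, right |
| 60 to 42 | 18/60 = 30% | 8.6 to 6.0 | -2.6/8.6 = -30.2% | responder, right |
| 40 to 20 | 20/40 = 50% | 5.7 to 2.9 | -2.8/5.7 = -49.1% | 50% non-responder, wrong |

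**Enumeration.** Baseline totals 28 to 63 and Week 4 totals 0 to 70 give 36 × 71 = 2556 pairs. At the 30% cut, 7 pairs are false non-responders and 5 are false responders. At the 50% cut, 4 of the 18 exact-50% pairs are lost and no pair goes the other way.

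**Missing days.** Five further day counts allowed by SAP 9.1 were enumerated (baseline/Week 4 days 6/7, 7/6, 7/5, 7/4, 6/6). Errors at the 50% cut then also run in reverse. For example, 25 over 6 days then 15 over 7 days has means 4.167 and 2.143, a reduction of 48.57%. Rounded, this is 4.2 to 2.1 = -50.0%, a responder.

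**Which rounding matters.** With unrounded means and only the percent change rounded, no pair was misclassified in any of the six day-count combinations.

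**How many subjects.** Complete diaries were simulated for 400,000 subjects per setting, with baseline mean 6.2 (SD 1.0). Figures are percent of subjects; false − is a lost responder and false + a gained one.

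| Mean change, SD of change, daily SD | 30%: false − / false + | 30%: rate unrounded to written | 50%: false − / false + |
|---|---|---|---|
| -1.5, 2.25, 0.8 | 0.51 / 0.50 | 43.79 to 43.78 | 0.27 / 0 |
| -2.5, 2.25, 0.8 | 0.50 / 0.49 | 60.91 to 60.90 | 0.32 / 0 |
| -2.0, 1.5, 0.8 | 0.75 / 0.72 | 53.85 to 53.81 | 0.40 / 0 |
| -1.5, 2.25, 0.3 | 0.58 / 0.41 | 43.94 to 43.77 | 0.22 / 0 |

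Misclassification at the 30% cut is thus 0.99% to 1.47%; 300 × 0.0099 = 3.0 and 300 × 0.0147 = 4.4. The largest net shift is 43.94 − 43.77 = 0.17 points. At the 50% cut it is 0.22% to 0.40%; 300 × 0.003 = 0.9.

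**The case against.** The best defence is that the rounding is for display. SAP 9.3.2 first defines a responder by a reduction of at least 30% in the mean, and the -30.0% line may only settle the sign. SAP 9.2.5 also rounds the scores it reports while building its total from unrounded ones. This leaves the sponsor's intent open, but not the text. Display precision has its own section (5.3.1), the rounding in 9.1 and 5.1.6 sits inside the derivations, and 9.2.5 shows that the SAP says so when it wants unrounded inputs. A programmer who follows 9.1 literally will produce the errors shown.

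The objection on consequence stands in full. These endpoints are exploratory (Protocol 5.3.3), the protocol planned only a descriptive responder summary (12.5.2), and SAP 5.6 makes no formal multiplicity adjustment.

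A reader might also infer more than the documents support:
- **That every subject at exactly 30% is lost.** With complete diaries, 2 of the 4 exact-30% pairs are lost. Subjects at exactly 30% were only 0.24–0.37% of those simulated, about 1 in 300; most errors fall near the cut.
- **That rounding twice is the cause.** Rounding the percent change alone did no harm.
- **That the 50% cut can only lose responders.** That fails once diary days are missing.
- **That the comparison with placebo is biased.** The rule is the same in every arm, and nothing in the documents suggests that it favours one.
- **That the primary analysis is in doubt.** Two roundings move a subject's change by at most 0.05 + 0.05 = 0.1 NRS points, against the planning SD of 2.25 in SAP 4.4.

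**Conclusion.** The point holds as a minor derivation flaw. That some identifiable diary totals receive the wrong status is exact arithmetic on the SAP's own rule, read literally. How many subjects this affects rests on the assumed diary distributions: about 1.0–1.5% at the 30% cut, nearly balanced in direction, and about 0.3% at the 50% cut, all lost responders when diaries are complete. Rates with missing days were not simulated.

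The responder table, the PGI-C composite and the Week 4 condition of sustained reduction inherit the error. The onset of response in SAP 9.3.3 uses four-day means, for which no rounding is stated, and is not counted here. None of this would be expected to change the trial's conclusion.

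**What to change.** Add one sentence to SAP 9.1: visit means are kept unrounded for deriving change, percent change and responder status, and are rounded only for display. Put the same wording in 5.1.6 for consistency, although that rounding caused no misclassification here. This removes the errors by construction and matches the SF-MPQ-2 rule in 9.2.5. It needs no new data and no extra analysis; the cost is the edit and a check that the analysis dataset stores the means unrounded.

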5.3.5.2 Analysis of Covariance Model

Using the change from baseline as a dependent variable, an analysis of covariance (ANCOVA) model with treatment (200 mg of NYX-2925, 50 mg of NYX-2925, 10 mg of NYX-2925, and Placebo) as the main effect and the baseline value as a covariate will be used to compare treatment groups at an individual analysis visit^[4]. The comparison of the NYX-2925 versus placebo will be assessed by forming the least squares means estimate of each particular NYX-2925 treatment groups stated in Section 5.2 and comparing them to the placebo group. The Kenward-Roger approximation will be used to estimate denominator degrees of freedom. Here is the SAS® code:

PROC MIXED DATA=ADAM ORDER=DATA METHOD=REML;

CLASS TRTP;

MODEL CHG = BASE TRTP / DDFM=KENWARDROGER;

LSMEANS TRTP / DIFF CL ALPHA=0.05;

/* -1 = Placebo; 0 = 10 mg of NYX-2925; 0.5 = 200 mg and 50 mg of NYX-2925 */

LSMESTIMATE "200 mg and 50 mg of NYX-2925 versus Placebo" TRTP 0 0.5 0.5 -1 / CL;

RUN:

The following ANCOVA model statistics for each treatment group will be presented in an analysis table:

- n =the number of records for that treatment or pooled treatment group
- Least Squares Mean for the treatment groups
- Standard Error for the treatment groups
- Least Squares Mean Difference for the NYX-2925 treatment groups versus Placebo
- Standard Error Difference for the treatment groups versus Placebo
- 95% Confidence Interval for the Difference for the treatment groups versus Placebo
- P-value for the Difference for the treatment groups versus Placebo

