6.2 Efficacy Population

The efficacy population will be based on subjects included in the safety population, were randomized, and have at least 4 post-baseline daily scores for the NRS assessment score assessing average pain intensity in the past 24 hours or at least one post-baseline visit (Week 2, Week 4, or Early Termination).

Subjects will be excluded from the efficacy population in the event a subject is given study drug by mistake without being randomized. This will also be classified as a major protocol violation.

Subjects in the efficacy population will be analyzed based on the planned treatment they were randomized to in the study. The efficacy population will be the primary analysis population used for this study.

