6.3 PP Population

The Per Protocol (PP) population will be based on all subjects in the efficacy population and the following criteria:

- Subjects received the same study drug throughout the duration of the study;
- Subjects received the same study drug to which they were randomized;
- Subjects met the randomization inclusion criteria described in Section 7.1 of the protocol;
- Subjects did not use any of the prohibited concomitant medications listed in Section 8.7 of the protocol;
- Subjects who have an overall study drug treatment compliance between 80% and 125%;
- Subjects have an observed mean NRS score assessing average pain intensity in the past 24 hours calculated within the Week 4 efficacy analysis visit window.

Subjects in the PP population will be defined based on a review of the relevant data by the Sponsor prior to database lock. However, subjects dispensed the wrong treatment arm (i.e., a treatment arm other than the one they were randomized to) will be removed from the PP population. Subjects in the PP population will be analyzed based on the planned treatment they were randomized to in the study.

7. Disposition, Baseline, and Other Characteristics

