9.1.2 Primary Efficacy Endpoint Analysis

The primary endpoint for mean change from baseline to Week 4 will be summarized with the same ANCOVA model described in Section 5.3.5.2. Additionally, 2 ANCOVA models will be provided for subjects using or not using at least 1 concomitant analysesic medication at Baseline^[4].

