14.1.1	All Subjects	Table: Analysis Populations		
14.1.2.1	Safety*	Table: Subject Disposition		
14.1.2.2	Efficacy*	Table: Subject Disposition		
14.1.2.3	PP	Table: Subject Disposition		
14.1.3.1	Safety*	Table: Demographics and Baseline Characteristics		
14.1.3.2	Efficacy*	Table: Demographics and Baseline Characteristics		

Number	Population*	TFL: Title
14.1.3.3	PP	Table: Demographics and Baseline Characteristics
14.1.4	Safety	Table: Medical History by System Organ Class and Preferred Term
14.1.5	Safety	Table: Prior Medications by ATC Class and Preferred Term
14.1.6	Safety*	Table: Questionnaire/Scale Assessments only at Screening or Baseline
14.2 Efficacy	y Data Summar	y Tables and Figures
14.2.1 Prima	ary Efficacy Dat	a
14.2.1.1.1	Efficacy*	Table: Mean Change and Percent Change from Baseline NRS Score Assessing Average Pain Intensity in the Past 24 Hours
14.2.1.1.2	PP	Table: Mean Change and Percent Change from Baseline NRS Score Assessing Average Pain Intensity in the Past 24 Hours
14.2.1.1.3	Efficacy	Table: Mean Change and Percent Change from Baseline NRS Score Assessing Average Pain Intensity in the Past 24 Hours (by Study Site)
14.2.1.1.4	Efficacy	Table: Mean Change and Percent Change from Baseline NRS Score Assessing Average Pain Intensity in the Past 24 Hours (by Age Groups)
14.2.1.1.5	Efficacy	Table: Mean Change and Percent Change from Baseline NRS Score Assessing Average Pain Intensity in the Past 24 Hours (by Gender)
14.2.1.1.6	Efficacy	Table: Mean Change and Percent Change from Baseline NRS Score Assessing Average Pain Intensity in the Past 24 Hours (by Race)
14.2.1.1.7	Efficacy	Table: Mean Change and Percent Change from Baseline NRS Score Assessing Average Pain Intensity in the Past 24 Hours (by Ethnicity)
14.2.1.1.8	Efficacy*	Table: Mean Change and Percent Change from Baseline NRS Score Assessing Average Pain Intensity in the Past 24 Hours (by Concomitant Analgesic Medications)
14.2.1.1.9	Efficacy	Figure: Mean Change from Baseline NRS Score Assessing Average Pain Intensity in the Past 24 Hours
14.2.1.2.1.1	Efficacy*	Table: Analysis of Covariance Model for Mean Change from Baseline NRS Score Assessing Average Pain Intensity in the Past 24 Hours (Observed Data)
14.2.1.2.1.2	PP	Table: Analysis of Covariance Model for Mean Change from Baseline NRS Score Assessing Average Pain Intensity in the Past 24 Hours (Observed Data)

Number	Population*	TFL: Title

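### The multiple-imputation code printed in SAP 9.1.3 bounds the change scores at 0 to 10, so no imputed day can show pain improvement, although the prose describes imputing daily scores

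*SAP*

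**What the plan says.** SAP 9.1.2 states: "The primary endpoint for mean change from baseline to Week 4 will be summarized with the same ANCOVA model", and SAP 5.3.5.2 fits that model "to compare treatment groups at an individual analysis visit". SAP 9.1 requires "at least 4 daily pain scores collected within a post-baseline analysis visit" before a weekly mean is formed, and adds "No missing data imputations will be used for these observed means", pointing to SAP 9.1.3 for imputation. If either value is absent, SAP 5.1.5 applies: "Otherwise the change from baseline will not be reported". The main result table (14.2.1.2.1.1 in SAP Section 13) is openly labelled as observed data.

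SAP 9.1.3 plans three imputation analyses: multiple imputation (Method 1), LOCF and BOCF. For Method 1 the two descriptions are:

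- **Prose:** individual missing NRS scores are imputed five times by MCMC, using planned arm and the scores on Days 1 to 28.
- **Code:** the PROC MI statement sets `MINIMUM=0` and `MAXIMUM=10`, and its variable list is treatment, baseline and `CHG1` to `CHG28`.

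The imputed data then pass through a PROC MEANS step run by imputation number and analysis visit only, and from there to PROC MIXED.

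**The concern.** Method 1 is the only multiple-imputation check on the observed-case primary estimate. SAP 5.1.5 defines change as post-baseline minus baseline, and SAP 9.3.2 treats a percent change of -30% or lower as a 30% pain reduction. Improvement is therefore a negative number, and a floor of zero on the change variables rules it out on every imputed day.

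An analysis run this way could disagree with the primary result even when the missing data are harmless. It could also appear to support a result that is wrong. The per-protocol analysis does not fill the gap, because that population requires an observed mean "calculated within the Week 4 efficacy analysis visit window" and so leaves out the same subjects.

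**Working it through.** **1. The plan's own figure.** SAP 4.4 gives a difference of 1.05, an SD of 2.25 and 75 per arm at two-sided alpha 0.05. The noncentrality is 1.05 / (2.25 × √(2/75)) = 1.05 / 0.367 = 2.86 on 148 df. Power is 81.0%, so the stated value of about 80% reproduces. The 1.05 and 2.25 are used again below.

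**2. What the bounds do.** For baseline b and a daily score from 0 to 10, change can run from -b to 10 - b. With b = 6, for example, that is -6 to +4. The printed limits allow 0 to +10. They exclude the whole improvement range, and they admit worsening that the scale cannot produce.

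**3. Where it applies.** SAP 9.1.3 uses imputed days only when the weekly mean could not already be calculated, that is, with 0 to 3 observed days in Days 22 to 28.

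- A subject with no observed Week 4 day always receives a Week 4 change of zero or more.
- A subject with 1 to 3 observed days can still have a negative mean. For example, three days at -4 and four imputed days at 0 give -12/7 = -1.7.

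**4. Illustration of size.** The following are assumptions, not figures from the documents: placebo mean change μ of -1 to -2; active mean μ - 1.05; normal daily changes with SD σ of 2.25 to 3.0; missingness at random; the whole Week 4 value imputed; no conditioning on the subject's other days.

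The share of values excluded is Φ(-μ/σ); the part above 10 is negligible. The mean of the bounded draws is T = μ + σ × φ(-μ/σ) / [1 - Φ(-μ/σ)].

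For μ = -1 and σ = 2.25:

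- Placebo: T = -1 + 2.25 × 0.3614/0.3284 = +1.48
- Active (mean -2.05): T = -2.05 + 2.25 × 0.2634/0.1811 = +1.22

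With a fraction m missing, each arm's mean becomes (1 - m) × true mean + m × T.

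- 15% missing in both arms: 0.85 × (-1.05) + 0.15 × (1.22 - 1.48) = -0.93
- 10% placebo, 20% active: [0.8 × (-2.05) + 0.2 × 1.22] - [0.9 × (-1) + 0.1 × 1.48] = -1.396 + 0.752 = -0.64

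| σ | Placebo μ | Excluded, placebo / active | Mean imputed change, placebo / active | 15% missing in each arm | 10% placebo, 20% active | 20% placebo, 10% active |
|---|---|---|---|---|---|---|
| 2.25 | -1 | 67% / 82% | +1.5 / +1.2 | -0.93 | -0.64 | -1.22 |
| 2.25 | -2 | 81% / 91% | +1.2 / +1.0 | -0.92 | -0.56 | -1.29 |
| 3.0 | -1 | 63% / 75% | +2.1 / +1.8 | -0.93 | -0.59 | -1.28 |
| 3.0 | -2 | 75% / 85% | +1.8 / +1.6 | -0.93 | -0.51 | -1.35 |

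The true difference is -1.05 throughout. Because missingness is random here, the observed-case comparison is unbiased, so the whole departure comes from the bounds. It can go in either direction. BOCF sets a missing Week 4 value to zero change; the printed Method 1 sets it, on average, to a worsening of about 1 to 2 points.

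**5. The averaging step.** PROC MEANS grouped by imputation and visit returns one mean per visit per imputation. It carries no subject, treatment or baseline, so PROC MIXED has no subject-level records to model.

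**The case against.** The strongest reply is that this is a programming slip in one sensitivity analysis. The prose already specifies scores, and a programmer would probably notice. The primary estimate is untouched. LOCF, BOCF and an MMRM over Weeks 1 to 4 (Protocol 12.5.1.2, SAP 9.2.2) are also planned, and SAP 9.3.2 counts a missing Week 4 mean as non-response. Nor would the code as printed produce the figures above, because the averaging step fails first. All of that stands, and it limits the weight of the point. It does not remove it: the SAP gives the code as the specification of Method 1, and code and prose cannot both be followed.

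A reader might go further and infer that an observed-case primary analysis is itself an error and that the MMRM must replace it. The documents do not support that. Protocol 12.5.1.1 names the Week 4 ANCOVA, Protocol 12.5.3 calls the primary analysis protocol-specified, and the SAP labels it openly. Under simulated pain-related dropout (75 per arm, assumed rates and mechanisms), the ANCOVA moved by about 0.02 to 0.16 NRS points. It moved further only when the link between pain and dropout was assumed to differ by arm (-1.21 to -1.27 against a true -1.05). Those mechanisms were missing at random by construction, which favours the MMRM.

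A reader might also infer that the trial is underpowered because SAP 4.4 makes no allowance for missing Week 4 means. The stated power reproduces, and any shortfall depends on a dropout rate that the documents do not give.

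**Conclusion.** SAP 9.1.3 Method 1 is wrong as printed. That follows from the text alone: the limits of 0 and 10 fall on change scores, and the SAP defines improvement as a negative change. The multiple-imputation analysis therefore cannot serve as a check on the observed-case primary ANCOVA.

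The size is illustrative and rests on the assumptions in step 4 of the working. The bounds exclude about 63-81% of plausible placebo values and 75-91% of active values. A true -1.05 becomes about -0.92 to -0.93 with 15% missing at random in each arm, and -0.51 to -0.64 with 10% missing on placebo and 20% on active. The primary estimate and the stated power are not affected. The choice of ANCOVA or MMRM as primary is a matter of judgement.

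**What to change.** Before unblinding, correct the Method 1 code in SAP 9.1.3:

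1. Impute the daily NRS scores for Days 1 to 28 with limits 0 and 10, as the prose says.
2. For each subject and imputation, derive the weekly mean from the scores and then its change from baseline. Keep the rule that a weekly mean already calculable from observed days is left alone.
3. Keep subject, treatment and baseline in the PROC MEANS step, so that PROC MIXED receives subject-level Week 4 records within each imputation.
4. Run the corrected code on dummy data before sign-off. Check that the imputed changes include negative values and that PROC MI accepts the treatment class variable together with the MCMC statement.

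The cost is a code correction and a test run, with no change to patients, visits or data collection. When the results are reported, read the already planned MMRM Week 4 contrast beside the observed-case ANCOVA. Making the MMRM primary would be an optional departure from the protocol, to be recorded in SAP 4.7 if chosen.
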